- General demographic and medical history forms
- Medical intake and comprehensive screening assessments performed by clinical research staff at Bellefield Towers or [name] (Oxford Building). Findings will be reviewed for eligibility and signed by a board-certified physician co-investigator ([name]) prior to the infusion. A drug test will also be obtained at intake; urine pregnancy tests may be obtained prior to fMRI scans at the MRRC.

Screening/baseline procedures include pre-infusion psychiatric evaluation, medical screening, and assessment battery (depression/emotional functioning assessments, neuroimaging, cognitive tasks)=1-2 visits over approximately 1-3 weeks

Infusion (ketamine or saline) visit (“Intervention Day 1” in consent form)=one visit, completed within approximately 1 week of baseline assessments

24-hours post-drug assessment battery (“Intervention Day 2” in consent form) (depression/emotional functioning assessments, neuroimaging, cognitive tasks)=one visit completed 24-hours after drug infusion

Cognitive training sessions and brief assessment battery (“Intervention Days 2,3,4,5” in consent form) (depression and suicidality assessments)=eight 15-20min sessions completed 2x/day (sessions separated by >=20 min) on days 1-4 post-infusion

Infusion +5-days assessment battery (“Intervention Day 6” in consent form) (depression/emotional functioning assessments, neuroimaging, cognitive tasks)=one visit completed following completion of all cognitive training sessions

Infusion +7 days remote (questionnaire) assessment (depression assessments)

Infusion +12 days assessment battery (depression/emotional functioning assessments, cognitive tasks)

Infusion +21 days remote (questionnaire/phone) assessment (depression and suicidality assessments)

Infusion +30-days assessment battery (depression/emotional functioning assessments, neuroimaging, cognitive tasks)

Infusion +2, 3, 4, 5, 6 & 12-months remote, naturalistic follow-up assessments (depression/emotional functioning assessments)=questionnaires completed monthly 2-6 months post-infusion and then once more at 12-months follow-up

Total duration of acute study period (after screening is completed)=approximately 4-5 weeks. Includes 1 infusion visit, 5 in-person assessment visits, 2 remote assessments, and 8 brief cognitive training sessions (twice-daily for 4 days post-drug infusion).

Total duration of naturalistic follow-up period=1-year.

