****Revised/additional exclusion criterion added on IRB's instruction, effective 08/07/2020 through the end of study****

- 19) Patients with diabetes

Rationale: For the duration of the COVID-19 pandemic, patients with diabetes, who are increased risk of serious complications from COVID-19 exposure, will be excluded.

Statistical Considerations and Statistical Analysis Plan

Sample Size

150 depressed adults will be enrolled in the study and randomized to one of the three treatment arms: ketamine + cognitive training (n=50); ketamine + sham training (n=50); or saline + cognitive training (n=50). Enrollment will continue until a final sample is acquired that includes the full target of n=150 patients who complete, at a minimum, (1) an infusion day, (2) a 24-hour assessment visit, and (3) $\geq 75\%$ of intended Neurocognitive Training (active or sham NT) visits, and will thus be considered to have received their NT allocation.

Power Analyses

Previous studies comparing intravenous ketamine to inert and psychoactive comparators (e.g., midazolam) report large effects at 24-hours ($d=.80$ for depression; $d>3$ for brain activation). The PI's previous mechanistic CT study in depression found large effects ($d=.7-1.0$) on symptom and performance-based cognitive measures. Clinically, we are interested in observation of moderate-large effects. The proposed design will yield 80% power to detect moderate effects based on comparisons of 100 ketamine and 50 saline patients ($d\geq .49$ and $r\geq .31$ using $\alpha=.05$). Based on comparisons of 50 patients in each of the ketamine+CT, ketamine+sham, and saline+CT conditions and 80% power, effects of $d\geq .57$ will be detectable (using $\alpha=.05$). Power for primary mixed effects analyses comparing treatment groups, which increases with additional repeated measures, will be higher than for such post-hoc single-point contrasts.

Analytic Plan

Infusion Phase. Mixed models regression with timepoint (baseline, infusion+24-hours) as a continuous within-subject factor, drug condition (ketamine vs. saline) as a fixed between-subject factor, and subject as a random factor will be applied to test hypothesized time*drug interactions on outcomes. For outcomes where time*drug interactions are observed, direction of effects within each drug condition will be disambiguated using baseline vs. post-infusion contrasts.

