Neurocognitive Training Phase. Mixed models regression with timepoint (24-hrs to 30 days) as a continuous within-subject factor, condition (ketamine+NT, ketamine+sham, saline+NT) as a fixed between-subject factor, and subject as a random factor will be applied to test hypothesized treatment and time*treatment interactions on outcomes. Saline+CT will serve as the reference group to test for enduring (main) effects of treatment and for time*treatment interactions.

Exploratory analysis 1 will extend mixed models analysis of depressive symptoms into the 12-month naturalistic follow-up using self-report (primary self-report outcome=QIDS-SR).

Exploratory analysis 2 will utilize a validated data-driven approach to identify integrative/combined moderators of CT effects (DV=MADRS slope), quantified as the optimal weighted combination of moderators (via elastic net w/cross-validation) across all primary + exploratory indices (e.g., fMRI, HNK/BDNF levels, etc.) assessed after ketamine (n=100), defining the data-driven, integrative brain state that optimizes benefit from CT.

Sensitivity analyses will be applied to all hypotheses to explore the impact of main and moderating effects of key biological variables: sex (stratified at randomization to ensure ~60%

female within-cell), age; and baseline clinical variables: treatment-resistance (stratified), concurrent medication.

Exploratory analyses will probe for generalization to other neurocognitive indices and self-report measures [e.g., depressive schemas (CTI); PROMIS measures; QIDS-SR; WHO Disability Assessment Scale].

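### The training-phase model names subject as its only random term; if that means an intercept alone and patients' slopes differ, the time-by-treatment standard error is too small

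*Combined protocol and SAP*

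**What the plan says.** The Neurocognitive Training Phase paragraph of the Analytic Plan describes a mixed model with continuous time from 24 hours to 30 days and "condition (ketamine+NT, ketamine+sham, saline+NT) as a fixed between-subject factor, and subject as a random factor will be applied". Two tests follow: "Saline+CT will serve as the reference group to test for enduring (main) effects of treatment and for time*treatment interactions".

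The Infusion Phase paragraph uses the same random term for a model with two timepoints, baseline and 24 hours: "subject as a random factor will be applied to test hypothesized time*drug interactions on outcomes". Neither paragraph names a random slope, a within-patient covariance structure, a degrees-of-freedom method or a robust standard error.

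Exploratory analysis 2 uses a patient-level slope as its outcome: it is to "identify integrative/combined moderators of CT effects (DV=MADRS slope"). Power Analyses calls the mixed models primary and relies on the repeated measures: "Power for primary mixed effects analyses comparing treatment groups, which increases with additional repeated measures, will be higher" than for single-point contrasts.

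The Summary of data collection timeline places cognitive tasks at days 1, 5, 12 and 30 after infusion, and neuroimaging at days 1, 5 and 30. Depression assessments are more frequent, for example "Infusion +7 days remote (questionnaire) assessment (depression assessments"), but the timeline does not name the instrument used at each visit.

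**The concern.** With two timepoints, a random slope cannot be separated from residual error, so in the infusion model the phrase can only mean a random intercept. The training-phase paragraph repeats it unchanged. An analyst who follows it literally would fit an intercept-only model, which sets the variance of patients' slopes to zero. Exploratory analysis 2 has a purpose only if slopes differ between patients.

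If they do differ, the intercept-only model treats part of the between-patient variation in slope as independent visit-level noise. Its standard error for a between-arm slope difference is then too small, and it would declare too often that an arm's course diverges from saline plus training. That comparison bears on the trial's question of durability. The extra visits that the plan counts on for power make the understatement worse.

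**Working it through.** **The plan's own figures.** A two-sided two-sample t test at α = .05 with 80% power gives d = 0.566 for 50 v 50 and 0.488 for 100 v 50. These reproduce the stated .57 and .49. Both are single-point contrasts; the documents give no variance or correlation for the mixed model.

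**Inputs from the documents.** 50 patients per arm; visits at days 1, 5, 30 (neuroimaging) or 1, 5, 12, 30 (cognitive tasks).

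**Assumed inputs.** Day-1 variance 1, split into residual variance σ² = .3, .5 or .7 and intercept variance 1 − σ². SD of true 29-day change τ = .3, .5 or 1.0, independent of day-1 level, so day-30 variance is 1.09, 1.25 or 2.00. No missing visits.

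**Formulas.** Scale time so that 29 days = 1. Let m be the number of visits and S the sum of squared centred times. Per patient:

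- true variance of the fitted slope = τ² + σ²/S
- variance reported by the intercept-only model (large-sample form) = σ²/S + τ²/(m − 1)
- SE ratio R = √(true/reported)
- type I error = 2[1 − Φ(1.96/R)]

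With m = 2 the two variances are equal, so the infusion model is unaffected. With m ≥ 3 and τ > 0 the reported variance is too small.

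**Worked case: four visits, σ² = .5, τ = .5.** Day 12 is the mean of days 1, 5 and 30, so S = 0.5874 for both visit sets. True: .25 + .5/.5874 = 1.1012. Reported: .8512 + .25/3 = .9345. R = √(1.1012/.9345) = 1.086. Error = 2[1 − Φ(1.805)] = 7.1%.

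**Type I error of one time-by-treatment contrast, intercept-only model**

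| Visits | σ² | τ = .3 | τ = .5 | τ = 1.0 |
|---|---|---|---|---|
| 3 | .7 | 5.4% | 6.1% | 8.5% |
| 3 | .5 | 5.6% | 6.5% | 9.4% |
| 3 | .3 | 5.9% | 7.3% | 10.9% |
| 4 | .7 | 5.6% | 6.5% | 10.2% |
| 4 | .5 | 5.8% | 7.1% | 11.7% |
| 4 | .3 | 6.3% | 8.3% | 14.3% |

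At τ = 0 every entry is 5.0%. A finite-sample residual term raises the entries by at most about 0.1 point. R runs from 1.018 (three visits, σ² = .7, τ = .3) to 1.338 (four visits, σ² = .3, τ = 1.0).

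**More visits.** At σ² = .5 and τ = .3 to 1.0, the error is 6.0% to 13.8% for days 1, 5, 12, 21, 30; 6.2% to 15.3% with day 7 added; and 6.7% to 19.9% with days 2 to 4 as well. Whether any depression instrument follows these schedules is not stated.

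**Simulation check.** With 20,000 null trials per case at σ² = .5 and τ = 0, .3, .5, .7, 1.0, the intercept-only test rejected in 4.8, 5.4, 6.3, 7.7, 9.2% (three visits) and 5.0, 5.7, 7.1, 9.0, 11.5% (four visits). The average-over-time treatment contrast stayed at 4.7% to 5.2% in all ten cases. A separate simulation of a test on patient slopes, which is equivalent to a random-slope model for complete balanced data, gave 4.3% to 5.5% throughout.

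**Treatment test if time is coded from day 1.** The condition coefficient is then the day-1 contrast. With mean time t̄ = 0.3793, its true variance per patient is (1 − σ²) + σ²(1/m + t̄²/S). The intercept-only model reports (1 − σ²) + τ²t̄² + σ²/m + t̄² × (reported slope variance). For three visits, σ² = .7 and τ = 1.0:

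- true: .3 + .7(.3333 + .2449) = .7048
- reported: .3 + .1439 + .2333 + .1439 × 1.6917 = .9206
- R = .875 and error = 2.5%

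Across the nonzero three- and four-visit cases the error is about 2.5% to 4.8%, so this test is conservative.

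**The case against.** **The premise is an inference.** A reader might conclude that the sponsor has chosen a model with inflated type I error. The documents do not support that: the text neither says random intercept nor rules out a random slope. The slope outcome in exploratory analysis 2 cuts both ways. It could come from a random-slope model that the authors already intend, or from per-patient regressions. That analysis is also exploratory and uses only the ketamine patients (n=100). It shows that slopes are expected to vary, not by how much. This stands, and the point is therefore conditional.

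**The size may be small.** Every variance above is assumed. At the smallest nonzero slope SD the error is only 5.4% to 6.3% for three or four visits. Figures of 10% or more for those schedules arise only when τ = 1.0, where outcome variance doubles by day 30. This also stands. The nine-visit figure should not be read as the trial's error rate.

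**Other tests.** A reader might infer that all the mixed-model tests are anti-conservative. They are not: with balanced data the average-over-time contrast and the infusion model are unaffected, and a day-1 condition coefficient errs on the conservative side. A reader might also infer that the power statement is false. The documents do not give enough to show that. For the slope test, added visits shrink σ²/S but not τ², so the gain has a ceiling.

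**What remains.** The wording permits two models with different standard errors for a primary test, and its literal reading gives the one that fails when slopes differ.

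**Conclusion.** The point holds in conditional form. If the training-phase model is fitted with a random intercept only and patients' slopes differ, the time-by-treatment test rejects too often. Under the stated assumptions, type I error at nominal 5% is about 5.4% to 11% with three visits and 5.6% to 14% with four, and more with longer series. There is no inflation if slopes do not vary. The direction follows from the algebra; the size cannot be fixed from the documents. Confidence is medium, because both the intercept-only reading and the variances are assumptions. This is something the sponsor should settle in the plan, not evidence that the analysis is wrong.

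**What to change.** Keep continuous time and the planned tests, and add wording such as:

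> The training-phase model includes, for each patient, a random intercept and a random slope for time with their covariance, fitted by REML with a small-sample degrees-of-freedom method (for example Kenward-Roger). If the fit does not converge, the time-by-treatment test is reported from the random-intercept model with cluster-robust standard errors by patient.

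Also state how time is coded for the treatment main-effect test, so that it is clear whether that test compares arms on average over the visits or at day 1. The infusion model needs no change.

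The fallback is best limited to non-convergence. At τ = .3 and σ² = .5, 28% to 30% of simulated three- and four-visit trials gave a singular fit. Keeping singular fits as they were gave 4.9% to 6.1% error in numerical REML fits, similar to switching to robust standard errors. Those fits used t with 147 degrees of freedom; Kenward-Roger itself was not run. Categorical time with an unstructured covariance is another valid choice, but it changes the form of the planned test.

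**Cost.** A few sentences in the plan and no new data. When slopes vary, time-by-treatment intervals are wider by R − 1, about 2% to 34% for three- or four-visit outcomes under these assumptions and more with more visits, so apparent power for that test falls.

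### The randomization strata (sex, treatment-resistance) are left out of the primary models, which costs a modest amount of power where the strata predict the outcome or its change

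*Combined protocol and SAP*

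**What the plan says.** The stratification is mentioned only in the sensitivity-analysis paragraph of the Analytic Plan. Those analyses cover all hypotheses and are to "explore the impact of main and moderating effects of key biological variables: sex (stratified at randomization", followed by age and by "baseline clinical variables: treatment-resistance (stratified), concurrent medication". No levels or cut-point are given for the treatment-resistance stratum.

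The two primary models are specified without either factor:

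- **Infusion Phase** (baseline and 24 hours): time plus "drug condition (ketamine vs. saline) as a fixed between-subject factor, and subject as a random factor will be applied". The effect tested is time*drug.
- **Neurocognitive Training Phase** (24 hours to 30 days): time plus "condition (ketamine+NT, ketamine+sham, saline+NT) as a fixed between-subject factor, and subject as a random factor will be applied". The effects tested are a treatment main effect and time*treatment.

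The Power Analyses section gives 80% power at d = 0.49 (100 vs 50) and d = 0.57 (50 vs 50). It describes these as single-point contrasts and expects the mixed models to do better.

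**The concern.** Stratified allocation removes stratum imbalance from the true sampling error of a contrast between arms. A model without the strata still leaves the variance they explain in its residual, so the reported standard error exceeds the real one. The intervals are then wider than they need be, the test runs below its nominal level, and some of the precision that stratification offers is not used.

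The planned power sits at 80% with 50 patients per arm in the training comparisons, so a few points are worth having. The plan will also produce stratum-adjusted results for every hypothesis, but only as sensitivity analyses. It does not say which result prevails if adjusted and unadjusted p-values fall on either side of 0.05.

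**Working it through.** **Inputs.** From Power Analyses: group sizes 100 vs 50 and 50 vs 50, d = 0.49 and 0.57, alpha 0.05. Assumed: two-sided tests, strata balanced across arms, and R2 (the share of outcome variance explained by the two strata) from 1% to 20%.

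**1. The plan's own figures.** With SD = 1, SE = sqrt(1/n1 + 1/n2) and power = Phi(d/SE − 1.96).

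- 100 vs 50: SE = 0.1732; 0.49/0.1732 = 2.829; power = Phi(0.869) = 80.8% (80.3% by noncentral t).
- 50 vs 50: SE = 0.2; 0.57/0.2 = 2.85; power = Phi(0.89) = 81.3% (80.6% by noncentral t).

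Both stated figures reproduce.

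**2. Between-subject contrasts.** Let k = sqrt(1 − R2). Under balanced strata the true SE is k times the unadjusted model's SE, so:

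- true size of the unadjusted test = 2 × (1 − Phi(1.96/k))
- power, unadjusted = Phi((d/SE − 1.96)/k)
- power, adjusted = Phi(d/(k × SE) − 1.96)

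For d = 0.49, 100 vs 50:

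| R2 | Unadjusted SE too large by | True size | Power, unadjusted | Power, adjusted | Loss (points) |
|---|---|---|---|---|---|
| 1% | 0.5% | 4.9% | 80.9% | 81.1% | 0.3 |
| 5% | 2.6% | 4.4% | 81.4% | 82.7% | 1.3 |
| 10% | 5.4% | 3.9% | 82.0% | 84.7% | 2.6 |
| 20% | 11.8% | 2.8% | 83.4% | 88.6% | 5.1 |

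The losses come from unrounded powers. For d = 0.57, 50 vs 50, they are 0.3, 1.3, 2.6 and 5.0 points.

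**3. The mixed-model effects.** With two timepoints and complete data, the time*drug estimate is the difference between arms in mean change. A stable effect of sex or treatment-resistance is the same at both timepoints and drops out. Random-intercept models were simulated to check this and the training phase (25 datasets per setting, intraclass correlation 0.5, complete data, balanced strata). Ratios of adjusted to unadjusted SE:

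| Effect | Strata added as main effects | Stratum-by-time terms also added, strata predicting change |
|---|---|---|
| Infusion phase, time*drug | 1.0000 | 0.98 to 0.93 |
| Training phase, time*treatment | 1.0000 | 0.995 to 0.98 |
| Training phase, condition coefficient | 0.97 or 0.93 | not the term of interest here |

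The 0.97 and 0.93 for the condition coefficient belong to strata that explain 10% and 20% of between-subject variance and do not predict change. When the strata did not predict change, adding stratum-by-time terms left the interaction ratios at 0.997 to 1.000.

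**The case against.** The strongest reply concerns scope. From the omission, a reader might infer that all primary standard errors are too large and all primary tests run below 5%. The documents do not support that. The only infusion-phase test and one of the two kinds of training-phase test are time-by-condition interactions, where the subject effect already absorbs stable stratum differences. The figures for size and power also belong to single-point contrasts, which the plan itself separates from its primary models. This part of the reply stands in full.

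Three further points:

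- **Prognostic strength is unknown.** Every patient has MADRS of at least 25 and at least one failed adequate trial, which may narrow what the strata can explain. This stands, and it is why the range starts at 1%.
- **Balance is assumed.** The plan gives no blocking scheme, and the target of 150 counts patients who reach minimum completion after randomization. Imbalance would bring the unadjusted test's size back towards 5%. It would not remove the benefit of adjusting: with no gain from balance at all, unadjusted power is the 80.8% of step 1, still below the adjusted figures.
- **The sensitivity analyses already look at stratum main effects for every hypothesis.** This is true, so the strata are not ignored. What remains is which analysis is primary, and the plan answers that with the unadjusted one.

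**Conclusion.** The point holds in a limited, conditional form. The primary models omit both stratification factors. If the strata predict the outcome, the standard errors for the training-phase treatment main effect and for single-point contrasts are too large. With balanced strata and an assumed R-squared of 1% to 20%, the cost for single-point contrasts is from under 1 to about 5 power points. The true size is about 4.4% to 3.9% at R-squared 5% to 10%.

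For time*drug and time*treatment there is a loss only if the strata predict change. In the settings simulated it was smaller in the training phase than in the infusion phase.

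A reader might also infer that the trial's conclusions are unsafe. They are not made so by this omission, which errs towards conservatism, does not inflate false positives and does not bias the estimates. This is a gain in efficiency available at almost no cost, not a threat to validity.

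**What to change.** Add a sentence to each model description in the Analytic Plan:

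- **Training phase:** include sex and the treatment-resistance stratum, as randomized, as main effects and with stratum-by-time terms.
- **Infusion phase:** include the same strata with stratum-by-time terms, since main effects alone cannot affect time*drug.

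State the levels of the treatment-resistance stratum, and name the adjusted model as primary. Keep the moderation tests (stratum-by-treatment) as sensitivity analyses.

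The cost is a few degrees of freedom out of 150 patients. If treatment-resistance has two levels (an assumption), that is two main-effect and two by-time terms, four in all per model. No new data or visits are needed.
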